9.2. Sample Size Determination

Approximately 32 participants will be screened to achieve 21 randomly enrolled to either GSK2982772 or placebo in a 2:1 allocation ratio. Replacement participants may be randomised (up to approximately 6) into the study at the discretion of the Sponsor, to ensure that approximately 21 have completed the Week 4 visit.

The primary efficacy endpoint is PASI75 response (achieving ≥75% improvement from Baseline in PASI score)at Week 12. The sample size is based on the difference in PASI75 response rates between GSK2982772 960 mg and placebo.

At Week 12, the expected PASI75 response rate on placebo is approximately 7%. This value represents typical responses seen in this indication [Papp, 2018; Checchio, 2017].

The study will leverage historical placebo data to reduce the uncertainty in the placebo response rate and thus improve operating characteristics of the trial. The historical placebo data will be combined with the trial data via a Bayesian analysis.

With a sample size of 21 participants there is approximately 99% probability of achieving a >97.5% posterior probability that the true treatment difference over placebo >0%, based on an assumed placebo response of 7% and an assumed true treatment difference of 55% and incorporating informative historical placebo data into the analysis. For the placebo arm an informative Beta (3.5, 46.5) distribution with an effective sample size of 50 participants was used. For the active arm a vague Beta (1/3, 1/3) prior is used.

An equivalent power calculation, assuming placebo response of 7% and using a two-sided significance level of 0.05, the proposed sample size of 21 participants gives >90% power to detect a 55% difference in PASI75 response rates between GSK2982772 960 mg versus placebo at Week 12 using a Newcombe score test [Newcombe, 1998] (assuming no historical data is borrowed).

No sample size re-estimation is planned for this study.

Note: "Enrolled" means a participant's, or their legally acceptable representative's, agreement to participate in a clinical study following completion of the informed consent process. Potential participants who are screened for the purpose of determining eligibility for the study, but do not participate in the study, are not considered enrolled, unless otherwise specified by the protocol.

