2. STATISTICAL HYPOTHESES / SUCCESS CRITERIA

The primary objective of this study is to estimate the efficacy of GSK2982772 960 mg MR QD compared with placebo following 12 weeks of treatment, this will be assessed using the estimates of PASI75 response at Week 12.

There will be no adjustment for multiplicity.

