3. SAMPLE SIZE DETERMINATION

Approximately 32 participants will be screened to achieve 21 participants randomly enrolled to either GSK2982772 or placebo in a 2:1 allocation ratio. Replacement participants may be randomised (up to approximately 6) into the study at the discretion of the Sponsor, to ensure that approximately 21 have completed the Week 4 visit.

The primary efficacy endpoint is PASI75 response (achieving $\geq 75\%$ improvement from Baseline in PASI score) at Week 12.

With a sample size of 21 participants there is approximately 99% probability of achieving a posterior probability of at least 97.5 that the true treatment difference over placebo is greater than zero. This is based on an assumed placebo response of 7%, an assumed true treatment difference of 55% and incorporating informative historical placebo data into the analysis. For the placebo arm an informative Beta (3.5, 46.5) distribution is assumed, with an effective sample size of 50 participants. For the active arm a vague Beta (1/3, 1/3) prior is used.

No sample size re-estimation is planned for this study.

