5.2.2. Main analytical approach

The primary analysis will be produced for the ITT population.

The summary measure of interest is the difference in PASI75 response rates at Week 12 (Day 85) between GSK2982772 and placebo. Missing values will be imputed as non-responders.

The primary endpoint will be analysed using a Bayesian logistic regression model, details given in [Table 2](#). Summary statistics will be provided for the posterior distribution of the true difference in PASI75 response rate (GSK2982772 vs placebo) as well as posterior probabilities for a range of thresholds.

A non-informative prior will be used for the PASI75 response rate on GSK2982772 and covariates.

An informative prior will be used for the placebo response rate of the form: 90% weight on $Be(5.39, 69)$ and 10% on $Be(1/3, 1/3)$. The prior was derived from historical data from similar clinical trials using meta-analytic predictive prior (MAP) approach, the effective sample size is approximately 63 [[Schmidli, 2014](#)].

In the event that the placebo prior is different from what is presented here, this will be documented in the CSR.

Table 2 Statistical Analysis of Primary Endpoint

Endpoint(s)	

 PASI75 response at Week 12 (Day 85) 	
Analysis Method	
Bayesian Logistic Regression (using informative prior)	
Model Specification	
Outcome	$y_i = \text{Response (0/1) for participant } i$
Predictors	
 Treatment (categorical) Prior Biologic Use (categorical) Baseline PASI score (continuous) 
Unless stated otherwise the predictors (not including study treatment) will be centered around their estimated mean prior to inclusion in the model

Model	$y_i \sim \text{Ber}(p_i)$ $\text{logit}(p_i) = (\text{Treatment=Placebo}) \times \beta_1 + (\text{Treatment=GSK}) \times \beta_2 + (\text{Prior Biologic Use}^*) \times \beta_4 + (\text{Baseline PASI score}^*) \times \beta_5$
Prior distributions for coefficients (β)	β = fixed effect parameters associated to predictors 
 β_1: informative prior such that $\text{logit}^{-1}(\beta_1) \sim$ mixture of Betas* β_2: non-informative prior such that $\text{logit}^{-1}(\beta_2) \sim \text{Beta}(1/3, 1/3)$ Other β_k: non-informative priors of $N(0, SD=100)$ 
*Expected prior is a mixture of $Be(5.39, 69)$ and $Be(1/3, 1/3)$, weighted to 90% and 10% respectively. Final prior will be reported in the CSR.

Model Checking & Diagnostics	
See Section 5.1.1	

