Results Presentation	

 Posterior medians and 95% CrI of true response rate for each treatment group. Posterior medians and 95% CrI for the true difference in proportion of responders (GSK2982772 – placebo) and odds ratios of GSK2982772 to placebo. Probabilities that the true treatment difference is greater than a range of values of interest (e.g. 0%, 20%, 45%, 55%). See OPS outputs list for details. Probabilities that the true response rate on active is greater than a range of values of interest (e.g. 0%, 30%, 55%). See OPS outputs list for details. 	
Interim Analysis	

The interim analysis will estimate the predictive probability of meeting various decision criteria including:
 
 >55% probability that true difference in PASI75 response (GSK2982772 – Placebo) above 45% >97.5% probability that true difference in PASI75 response (GSK2982772 – Placebo) above 0% 	

Predictive probabilities will be calculated via simulation assuming a total sample size of 21 (14:7 for GSK2982772:Placebo).

The parameter posterior distributions from the Bayesian logistic regression analysis of interim data will be used to simulate predicted PASI75 responses for remaining trial subjects. For participants yet to be enrolled, average covariate values will be assumed.

The predicted data will be combined with the observed interim data and the Bayesian logistic model applied to assess the decision criteria. This process will be repeated for each run of the MCMC procedure. The proportion of times the decision criteria is met will be the predicted probability.

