5.2.3. Sensitivity analyses

Where informative priors have been used, a sensitivity analysis using vague priors (no historical borrowing) will also be produced.

Additional sensitivity analyses to assess the impact the missing data handling for binary data may be produced, such as using a LOCF approach to missing data.

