5.2.5. Subgroup analyses

No formal subgroup analysis is planned. Descriptive statistics in the form of a frequency table of PASI75 response by prior biologic use will be produced.

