5.3.2. Main analytical approach

Categorical endpoints

The proportion of participants achieving additional PASI responder endpoints of interest (PASI50/90/100) will be summarised by treatment arm and visit. Missing values will be imputed as non-responders. Credible intervals for response rates will be included (using $Be(1/3, 1/3)$ prior for all treatment arms and visits).

The sIGA scores will be summarised as categorical data with the proportion of participants achieving each sIGA score being presented by treatment group and visit. The proportion of sIGA **cci** (0) or **cci** (1) will also be presented, with missing values imputed as non-responders. Credible intervals for response rates will be included (using $Be(1/3, 1/3)$ prior for all treatment arms and visits).

Line plots of proportion of responders (with 95% CrI) over time by treatment group will be produced for both PASI and sIGA responder endpoints.

A Bayesian logistic regression approach will be used to assess response rates at Week 12, details given in [Table 3](#).

Continuous endpoints

Both secondary and exploratory objectives of BSA and PASI score will be investigated using the same Bayesian repeated measures model (MMRM) analysis.

Summary statistics by treatment and visit will be provided for change from baseline in both PASI score and BSA. A summary of percentage change in PASI will also be provided.

A Bayesian MMRM approach will be used to account for the repeated visits (details given in [Table 4](#)). This approach assumes missing values are MAR.

Line plots of posterior means (\pm SD) from the MMRM analysis over time by treatment group will be provided.

Table 3 Statistical Analysis of Categorical Secondary Endpoint(s)

Endpoint(s)	

 • Proportion of PASI50, PASI90 and PASI100 responders at Week 12 (Day 85) • Proportion of sIGA ^{CCI} (0) or ^{CCI} (1) at Week 12 (Day 85) 	
Analysis Method	
Bayesian Logistic Regression	
Model Specification	
Outcome	y_i = Response (0/1) for participant i
Predictors	
 • Treatment (categorical) • Prior Biologic Use (categorical) • Baseline score (sIGA to be treated as continuous) 
Unless stated otherwise the predictors (not including study treatment) will be centered around their estimated mean prior to inclusion in the model

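### The approximately 99% sizing figure does not describe the covariate-adjusted primary model with N(0, SD=100) priors, which at 62% vs 7% gives a noisier estimate and about 90-92% interval coverage

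*SAP*

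**What the plan says.** SAP 5.2.2, Table 2, makes the primary model a Bayesian logistic regression with one term per arm, prior biologic use and centred baseline PASI. The active rate has a Beta(1/3, 1/3) prior. The placebo rate has a mixture prior, 90% Beta(5.39, 69) and 10% Beta(1/3, 1/3). The two covariate coefficients have "non-informative priors of $N(0, SD=100").

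The sizing statement is in SAP section 3: "With a sample size of 21 participants there is approximately 99% probability of achieving a posterior probability" of at least 97.5% that the difference exceeds zero, at 7% on placebo and a 55% difference. Protocol 9.2 adds: "For the placebo arm an informative Beta (3.5, 46.5) distribution with an effective sample size of 50 participants was used". Both give Beta(1/3, 1/3) for the active arm. Neither mentions covariates.

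The aim is estimation. SAP section 2 says: "The primary objective of this study is to estimate the efficacy of GSK2982772 960 mg MR QD compared with placebo". Table 2 will report "Probabilities that the true treatment difference is greater than a range of values of interest (e.g. 0%, 20%, 45%, 55"%).

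On checks, SAP 5.2.3 says that "a sensitivity analysis using vague priors (no historical borrowing) will also be produced". SAP 5.2.5 adds: "Descriptive statistics in the form of a frequency table of PASI75 response by prior biologic use will be produced". For PASI50/90/100 and sIGA, SAP 5.3.2 says: "Credible intervals for response rates will be included (using $Be(1/3, 1/3)$ prior for all treatment arms and visits").

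**The concern.** At 62% vs 7% the expected number of responders is 14 × 0.62 + 7 × 0.07 = 9.2, and four coefficients are fitted. One prior standard deviation for a covariate is a log-odds shift of 100, so the prior restrains almost nothing. In small arms the covariates often separate responders from non-responders, wholly or partly. The data from that arm then do not bound the coefficients, and neither does the prior.

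Two things are at stake. The quoted success probability may belong to a different model from the one that will be run. The reported difference may be noisier than it needs to be, with an interval that does not widen to match. The planned prior sensitivity analysis removes historical borrowing and leaves the covariate priors alone, so it would not show the problem.

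**Working it through.** **Inputs from the documents.** 14 active and 7 placebo (Table 2, interim section); true rates 62% and 7% (SAP section 3); criterion Pr(difference > 0) > 97.5%; priors as above; 95% equal-tailed intervals (SAP 5.1); rates read at average covariates (SAP 5.1.1).

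**Assumed, because the documents give no values.** Prior biologic use 15%, 30% or 50%, balanced across arms; baseline PASI 12 plus a gamma variable, mean 20, SD 6.5; no covariate effect unless stated.

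**Step 1: the plan's own figure.** Without covariates the active posterior is Beta(1/3 + yA, 1/3 + 14 − yA) and the placebo posterior is Beta(3.5 + yP, 46.5 + 7 − yP). For each of the 15 × 8 outcomes, Pr(difference > 0) = ∫ f_P(p)[1 − F_A(p)] dp. Summing Bin(yA; 14, 0.62) × Bin(yP; 7, 0.07) over outcomes where this exceeds 0.975 gives **99.7%**, consistent with approximately 99%.

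**Step 2: change only the placebo prior.** With the Table 2 mixture and still no covariates, exact enumeration gives 98.1%, coverage 96.5% and RMSE 0.130. The prior change therefore costs 99.7 − 98.1 = 1.6 points.

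**Step 3: add the covariates.** logit(p) = β1·placebo + β2·active + β4·biologic + β5·PASI, with D = expit(β2) − expit(β1) at centred covariates. The posterior was integrated on a grid, with 600 to 1000 simulated trials per row. Monte Carlo SE is about 0.9-1.2 points for coverage and 0.6-1.1 for the criterion.

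| 62% vs 7% | Covariate prior | Coverage | >0 criterion met | RMSE |
|---|---|---|---|---|
| 30% biologic use | N(0,100) | 89.7% | 96.3% | 0.175 |
| | N(0,1), standardised | 92.9% | 97.9% | 0.144 |
| 15% use | N(0,100) | 90.2% | 94.3% | 0.186 |
| | N(0,1) | 93.3% | 98.2% | 0.141 |
| 50% use | N(0,100) | 92.5% | 97.7% | 0.165 |
| | N(0,1) | 94.8% | 98.7% | 0.139 |
| 30% use, prognostic* | N(0,100) | 89.5% | 92.5% | 0.185 |
| | N(0,1) | 95.5% | 98.2% | 0.144 |
| Unadjusted, exact | none | 96.5% | 98.1% | 0.130 |

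*Log-odds −1 for biologic use and −0.5 per SD of PASI.

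N(0, 2.5) gave coverage of 91.6%, 92.2% and 93.3% at 30%, 15% and 50% use. Separately coded simulations agree. One, with 2000 trials per case, 20-50% biologic use and PASI SD 7, gave coverage of 89-91% and the criterion met in 95-97%. Shorter runs of 280 to 938 trials gave coverage of 90.6-92.1% and RMSE of 0.154-0.175.

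**Step 4: mechanism.** With 14 active participants and 30% biologic use, the covariates alone separated the active-arm outcomes, completely or partly, in about 18% of simulated trials at a 62% rate and 33% at 27%. With six active participants, the minimum for the interim analysis, this was about 70-80%. The PASI scale is not the cause: N(0,100) per point and per SD gave identical results in 200 trials.

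**Step 5: other truths (30% use).**
- 27% vs 7%, a 20% difference: >0 criterion met in 31.5% (29% in a repeat run), against 50.7% exact unadjusted and 41.5% with N(0,1). Coverage 86.9% against 96.7%.
- 7% vs 7%: criterion met in 0.4%, against 1.25% unadjusted.
- 62% vs 7%, the Table 2 interim criterion of more than 55% probability of a difference above 45%: met in 74.7% against 75.1% unadjusted in the same trials; 77% against 74% exact in a smaller run.
- 18:9, all six replacements, 62% vs 7%: coverage 93.0% (SE 0.9) against roughly 94%, RMSE 0.138 against 0.115.

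**The case against.** Much of the case on the other side stands.

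- The documents do not say that the sizing had no covariates. That is inferred from the listed inputs and from the covariate-free model reproducing the figure.
- The placebo-prior change was foreseen in protocol 9.4.1 and accounts for 1.6 points. The covariates account for 98.1 − 97.7 = 0.4 to 98.1 − 94.3 = 3.8 points when they have no true effect.
- Neither document promises frequentist coverage at a fixed truth, and the benchmark is discrete. One outcome, 12/14 vs 0/7 with probability 2.55%, lies almost on the interval limit and moves unadjusted coverage between about 94.0% and 96.5%.
- Most rows assume no covariate effect, which favours shrinkage. The prognostic row still favoured N(0,1).

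A reader might infer more than the documents support:

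- **That the trial is badly undersized, or its go/no-go compromised.** At 62% vs 7% the >0 criterion is still met in about 93-98% of trials and the 45% criterion hardly moves. A clear fall in the latter (59% against 71%) needed assumed effects of −2.5 for biologic use and −1 per SD of PASI, which no document supports.
- **That false positives rise.** They fall.
- **That a 20% difference is a planning scenario.** It is a reporting threshold; the only design alternative is 55%.
- **That no unadjusted PASI75 interval is planned anywhere.** Protocol 9.4.2 mentions Newcombe intervals for group differences, but after a sentence on PASI50/90/100, so its reach to PASI75 is unclear. SAP 5.3.2 plans line plots with credible intervals for PASI responder endpoints, but per arm and not for the difference. The SAP names no unadjusted PASI75 difference with an interval.

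**Conclusion.** The point holds in a limited form. The approximately 99% matches a two-arm model without covariates and with Beta(3.5, 46.5), and neither document gives operating characteristics for the Table 2 model. At the design alternative, the cost in success probability is modest. The cost in estimation is clearer: coverage falls to about 90-92%, and RMSE rises from 0.13 to about 0.15-0.19. In the simulations, tightening the covariate prior recovered most of the RMSE loss and about half of the coverage loss. The remainder is the price of adjusting for two covariates at this size. Confidence is high in the direction and medium in the exact coverage, because every covariate distribution is assumed. At 18:9 the coverage gap is within simulation error, though the RMSE gap remains.

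**What to change.** 1. In SAP section 3 and protocol 9.2, state that approximately 99% refers to the two-arm model with Beta(3.5, 46.5) and no covariates, if the sponsor confirms this. Give the corresponding figure for the Table 2 model and mixture prior under stated covariate assumptions.
2. In SAP 5.2.3, add the unadjusted Beta-binomial PASI75 difference with its 95% credible interval, using the same placebo mixture.
3. In Table 2, at interim and final, standardise baseline PASI and use a weakly informative covariate prior such as N(0, SD=1). N(0, 2.5) recovers less of the loss. Keep the adjustment for prior biologic use, the stratification factor.

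The cost is wording, one prior specification, one extra output and a short simulation, all before unblinding. There are two downsides: large true covariate effects are shrunk somewhat (bias −0.008 in the prognostic case with N(0,1)), and the stated success probability becomes slightly less favourable.

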4. ANALYSIS SETS

Analysis Set	Definition / Criteria	Analyses Evaluated
Screened	
 • All participants who were screened for eligibility 	
 • Study Population
Enrolled	
 • All participants who signed the ICF, passed screening and were eligible for randomisation (regardless of whether the participant went on to be randomised). • Note screening failures (who never passed screening even if rescreened) and participants screened but never enrolled into the study (Reserve, Not Used) are excluded from the Enrolled analysis set as they did not enter the study. 	
 • Study Population
Randomised	
 • All participants who were randomly assigned to study intervention in the study. • Participant must have signed ICF and passed Screening. 	
 • Study Population

Analysis Set	Definition / Criteria	Analyses Evaluated
	
 • Data will be reported according to the randomised study intervention. 	
Intent to Treat (ITT)	
 • All participants who were randomised to study intervention in the study and who received at least one dose of study intervention. • Data will be reported according to the randomised study intervention. 	
 • Efficacy
Modified Intent to Treat (ITT)	
 • All participants in the ITT population who completed at least the Week 4 assessment. • Data will be reported according to the randomised study intervention. 	
 • Efficacy
Safety	
 • All participants in the enrolled population who received at least one dose of study intervention. • Data will be reported according to the actual study intervention received. 	
 • Safety • PD
COVID-19	
 • All participants in the Safety set who had a confirmed, probable or suspected COVID-19 case diagnosis. 	
 • COVID outputs

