5.8. Interim Analyses

An interim analysis (IA) is planned to occur when at least six participants on GSK2982772 have completed the Week 12 (Day 85) visit or withdrawn from study treatment. The purpose of the IA is for internal decision making about future GSK2982772 trials and assess futility. The study may be stopped for futility if the probability of a positive outcome at the end of the trial is low based on the data available at the IA. The trial cannot be stopped early based on positive efficacy data.

Predictive probabilities will be calculated via simulation. The parameter posterior distributions from the Bayesian logistic regression analysis of interim data will be used to repeatedly simulate PASI75 response for remaining trial subjects. The predicted data will be combined with interim data to assess end of study criteria and calculate the proportion of times the decision criteria are met.

The data will be reviewed by an internal Data Review Committee. The committee will include the study statistician, the study pharmacokineticist and a limited number of GSK staff. A DRC charter will identify the specific staff to form part of the DRC, as well as detail the data to be reviewed, planned analyses, guidelines for the decision rules to be followed and a dissemination plan for interim decisions.

A subset of the outputs for the end of study will be produced for the IA. These will focus on efficacy data including, but not limited to:

- Summaries of PASI response data and change from baseline in PASI score by treatment and visit as outlined in Section [5.3.2](#) (Modified ITT population).
- Bayesian analysis of PASI75 response at Week 12 (Day 85) as outlined in Section [5.2.2](#) (Modified ITT population).
- Summaries of PK data and predicted target engagement as outlined in Section [5.5](#) (PK population).
- Summary of longitudinal model used to predict PASI score and the derived PASI75 at Week 16, outlined in Section [5.5.1](#), (conducted by CPMS on the ITT population).
- Summaries of disposition and psoriatic baseline characteristics (Randomised population).

Safety monitoring of blinded data will be conducted by the internal GSK Safety Review Team (SRT) at regular intervals throughout the study, see Section 8.2 of Protocol.

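### The interim predictive probability is built on Modified ITT and fixed at 14:7, so if dosed early losses are replaced it may no longer describe the primary ITT analysis, and the 45-point figure comes out too high

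*SAP*

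**What the plan says.** - **Interim simulation (SAP 5.2.2, Table 2).** "Predictive probabilities will be calculated via simulation assuming a total sample size of 21 (14:7 for GSK2982772:Placebo". The two listed criteria are a posterior probability above 97.5% that the difference exceeds 0, and one above 55% that it exceeds 45 percentage points.
- **Interim data set (SAP 5.8).** The listed output is "Bayesian analysis of PASI75 response at Week 12 (Day 85) as outlined in Section [5.2.2](#) (Modified ITT population". SAP 4 defines that set as "All participants in the ITT population who completed at least the Week 4 assessment".
- **Final primary analysis (SAP 5.2.2).** "The primary analysis will be produced for the ITT population", and "Missing values will be imputed as non-responders". SAP 4 defines ITT as "All participants who were randomised to study intervention in the study and who received at least one dose of study intervention".
- **Replacement (SAP 3; also Protocol 9.2).** "Replacement participants may be randomised (up to approximately 6) into the study at the discretion of the Sponsor", the purpose being "to ensure that approximately 21 have completed the Week 4 visit".

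No section removes a replaced participant from ITT. No section says which final population the predictive probability refers to, or how replaced participants enter it.

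**The concern.** Protocol 9.5 and SAP 5.8 tie futility to the chance of a positive outcome at the end of the trial. The natural reading is a positive primary analysis, which is on ITT. The interim is set up around Week 4 completers, and 21 is the size that the replacement rule aims at for that group.

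Once dosed participants are lost before Week 4 and replaced, the two sets separate. The lost participants are absent from the interim model but sit in the final ITT denominator as certain non-responders. A predictive probability that leaves them out is too favourable for any criterion requiring a high active response rate. Both uses of the interim, the futility decision and planning of later trials, would rest on it.

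The case is not remote. The protocol's amendment history records that the replacement allowance was doubled from about 3 to about 6 because the pandemic was expected to affect retention.

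**Working it through.** **Inputs from the documents**
- Active prior Beta(1/3, 1/3); placebo prior 0.9 Be(5.39, 69) + 0.1 Be(1/3, 1/3) (SAP 5.2.2).
- Planned final size 14:7; up to about 6 replacements; allocation 2:1.
- Design rates: placebo 7%, active 7% + 55% = 62% (SAP 3).

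**Assumptions, since the documents give no figures**
- No covariates, so the posteriors are conjugate.
- Interim data on 6 active and 3 placebo completers, with no placebo responders.
- All replaced participants were dosed and left before Week 4. Their main split is 2:1.

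**Step 1: reproduce the plan's own figure.** Sum Binomial(14, 0.62) × Binomial(7, 0.07) over all outcomes for which the posterior probability of a difference above 0 exceeds 0.975. The result is 0.997 with the Beta(3.5, 46.5) prior of SAP 3 and 0.981 with the mixture prior. The SAP states about 99%, so the set-up reproduces it.

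**Step 2: size of ITT.** Six replaced participants give 21 + 6 = 27. At 2:1 the losses are 4:2, so the final sizes are 14 + 4 = 18 and 7 + 2 = 9. Three replaced participants (2:1) give 16:8.

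**Step 3: active responders needed at the end.** For the 45-point criterion with 0 or 1 placebo responders, the minimum is 8 of 14, 9 of 16 or 10 of 18. For the above-zero criterion with no placebo responders it is 4 in all three cases.

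**Step 4: predictive probability.** With x active responders of 6, future active responders follow a beta-binomial with parameters 1/3 + x and 1/3 + 6 − x. Future placebo responders follow the updated mixture. The predictive probability is the sum of these joint probabilities over outcomes that meet the final criterion.

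The number still to be simulated is the same in both cases: 14 − 6 = 8 active and 7 − 3 = 4 placebo as planned; 18 − 4 − 6 = 8 and 9 − 2 − 3 = 4 at 18:9. Only the certain non-responders in the denominator differ. With 4 of 6 responders, the remaining 8 active participants must supply 8 − 4 = 4 responders as planned, 9 − 4 = 5 at 16:8, and 10 − 4 = 6 at 18:9.

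| Criterion | Active responders of 6 | Planned 14:7 | ITT 16:8 (2:1 replaced) | ITT 18:9 (4:2 replaced) |
|---|---|---|---|---|
| Above 45 points | 2 | 0.091 | 0.032 | 0.007 |
| | 3 | 0.409 | 0.238 | 0.109 |
| | 4 | 0.806 | 0.655 | 0.471 |
| | 5 | 0.978 | 0.940 | 0.868 |
| Above 0 | 1 | 0.242 | 0.217 | 0.217 |
| | 2 | 0.702 | 0.664 | 0.664 |
| | 3 | 0.955 | 0.942 | 0.942 |

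The largest shifts at 18:9 are 0.806 − 0.471 = 0.335 for the 45-point criterion and 0.702 − 0.664 = 0.038 for the above-zero criterion.

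**Step 5: range.** In the extreme case where all six replaced participants and their replacements are on active (20:7), the 45-point figure with 4 of 6 responders is 0.275, and the above-zero figure with 2 of 6 is 0.467. Using Beta(3.5, 46.5) for placebo, the 2:1 results are nearly the same (0.807 against 0.472 for 4 of 6).

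**Step 6: the same effect at the design rates.** The chance of meeting the 45-point criterion at the end is 0.74 at 14:7 and 0.32 at 18:9 with 4:2 counted as non-responders. For the above-zero criterion it is 0.981 and 0.984.

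**The case against.** The strongest reply is that 14:7 is deliberate. The interim model is on Modified ITT, the replacement rule aims at about 21 Week 4 completers, and SAP 5.2.4 allows the primary analysis to be repeated on Modified ITT. On that reading the simulation matches its own population. This explains where 21 comes from, but it does not settle the point: the Modified ITT analysis is supplementary and optional, the primary analysis is ITT, and nothing says that the predictive probability targets the supplementary one.

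Three further replies stand and limit the point. Replacement is optional and at the sponsor's discretion. Replacing someone who was randomised but never dosed does not enlarge ITT. The decision rules are left to the Data Review Committee charter, which is not among the documents, and no futility cut-off is given.

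A reader might also infer that known losses use up places among the 21, so that the above-zero figure is too low and the trial could be stopped wrongly. That would require the early losses to be in the interim data as observed non-responders. SAP 5.8 puts the interim model on Week 4 completers, so they are not there, and the error runs towards optimism.

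**Conclusion.** The point holds in conditional form. If dosed participants lost before Week 4 are replaced, the planned figure does not describe the primary ITT analysis. Under the stated assumptions it overstates the 45-point criterion by 30 to 34 points with six replaced and 3 or 4 of 6 active responders, and by about 15 to 17 points with three replaced. The above-zero criterion hardly moves when losses split 2:1; it moves more only if losses fall heavily on active.

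Two stronger conclusions are not supported. It cannot be said that an analysis of 21 will not take place: with no early losses and no replacement, ITT is about 21 and 14:7 fits, and a Modified ITT analysis of about that size may be produced. (If early losses are left unreplaced, the total of 21 still fits ITT, but those participants must be carried as non-responders rather than simulated.) Nor can it be said that a stop or continue decision would change, because no cut-off is stated. The sizes depend on the assumed 6:3 interim, the absence of covariates and the split of losses.

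**What to change.** Amend Table 2 and SAP 5.8 together, since changing only the sample-size sentence would leave the Modified ITT specification in conflict with it:

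1. State that the predictive probability targets the final ITT primary analysis.
2. Simulate to 21 plus the dosed participants already replaced or approved for replacement at the interim, using actual arm counts where known and the randomised ratio otherwise.
3. Carry known early discontinuers as non-responders in the simulated final data, even though they are outside the interim Modified ITT set.
4. Report the 14:7 Modified ITT figure alongside, labelled as such.

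The cost is a few SAP sentences and a changed input to the simulation, with no effect on participants or data collection. The price in results is a less favourable 45-point predictive probability whenever replacements have occurred.
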